11.5. Baseline Visit (0 – 7 days post Baseline Period)

At the Baseline Visit, subjects will return to the clinic to complete all screening requirements. Any adverse since the last study visit will be collected.

The following assessments, as outlined in Table 11.1-1, will be conducted:

- Demographics
- Medical history
- Beck Depression Inventory (BDI-II)
- Oswestry Disability Index (ODIv2.1a)
- Short Form Health Survey 36 (SF-36v2)
- EQ-5D 5-Level
- Resource Utilization Inventory (RUI)
- Work Productivity (WPAI-SHP v2.0)
- Pain Intensity: VRS
- Pain Intensity: NRS

Subjects that meet all study criteria will be scheduled for the device implant procedures (trial and permanent implant of the SCS system). If a subject fails to meet all the eligibility criteria, they will be withdrawn from the study.

End of Visit Information:

- Subjects should be reminded not to make any changes to their opioid medications.

11.6. Implant Procedures (Up to 90 days following the Baseline Visit)

Subjects will have up to 90 days following the Baseline Visit to receive their Spectra WaveWriter System. Subjects will undergo a trial procedure per standard of care. Following a successful trial, i.e. at least 50% pain reduction in their overall pain as compared with Baseline, the subject will proceed to permanent implantation. Subjects with an unsuccessful implant procedure will be followed for 2 weeks for procedure related adverse events then withdrawn from the study. Acute opioid pain medications may be taken.

11.7. Healing Period (0 - 28 days following Implant Procedures)

The subject’s device will remain inactivated (device OFF) for up to 28 days following the permanent implantation procedure to allow for healing. Acute opioid pain medications may be taken during this period. No additional scheduled assessments will be completed during this period.

11.8. Activation Visit (Day 0)

At the Activation Visit, the subject’s Spectra WaveWriter SCS System will be activated. Any adverse events since the last study visit will be collected.

Subjects must stop taking acute opioid pain medications, as applicable, and are not to make any changes to their opioid pain medications up to the 3-Month Visit.

Information regarding programming parameters will be documented. To aid in programming it is recommended that thoracic and/or lumbar imaging is obtained at this visit or up to 7 days prior to the visit to show the position(s) of the study device lead(s). In the event of suspected lead migration, imaging may be performed to document lead positions.

End of Visit Information:

- Subjects will receive instructions on the use of the device including the Remote Control and charging system.
- Subjects should be instructed to evaluate all programs saved on the Remote Control prior to their next visit as applicable.
- Subjects are to contact the site in an event that any additional intervention is warranted, to report a complaint and/or a suspected adverse event, reprogramming, etc.
- Subjects should be reminded not to make any changes to their opioid pain medications.

11.9. Programming Period (Up to 70 days following the Activation Visit)

Following device activation, subjects’ device will be optimized to achieve effective therapy during the Programming Period of up to 70 days post-activation.

During this period, subjects may return as many times as needed (unscheduled visits) for optimization of programming.

Information regarding programming parameters and device information may be collected and documented.

11.10. Programming Lock Visit (Day 70 ± 14 days)

At the Programming Lock Visit, subjects will return to the clinic to have their programs locked. Any adverse events since the last study visit will be collected.

It is recommended that their final settings be documented in the study records. No further changes to the subjects programs such as electrode configuration will be allowed except to resolve a device and/or stimulation-related AE.

At this Visit, subjects will choose their preferred programs (or modalities) to be evaluated during the Evaluation Period. Subjects' choice will be documented.

Information regarding programming parameters and device information may be collected and documented.

End of Visit Information:

- Subjects will receive instructions on the use of the device including the Remote Control and charging system, as needed.
- Subjects should be instructed to evaluate their preferred programs (or modalities) prior to their next visit.
- Subjects are to contact the site in an event that any additional intervention is warranted, to report a complaint and/or a suspected adverse event, reprogramming, etc.
- Subjects should be reminded not to make any changes to their opioid medications.

11.11. *Evaluation Period*

During the Evaluation Period, subjects will evaluate each of the programs (or modalities) previously chosen at the Programming Lock Visit.

11.12. *3-Month Visit (90 + 14 days)*

During the 3-Month Visit, subjects will return to the clinic for study evaluations and programming. Any adverse events since their last study visit will be collected.

The following assessments will be completed as summarized in Table 11.1-1:

- Beck Depression Inventory (BDI-II)
- Oswestry Disability Index version 2.1a (ODI v2.1a)
- Short Form Health Survey 36 items (SF-36 v2)
- EQ-5D 5-Level
- Resource Utilization Inventory (RUI)
- Work Productivity (WPAI-SHP v2.0)
- Pain Intensity: VRS
- Pain Intensity: NRS
- Clinical Global Impression of Change (CGI-C)
- Patient Global Impression of Change (PGI-C)
- Percent Pain Relief (PPR)

- Preference Questionnaire
- Treatment Satisfaction Questionnaire for Medication - modified (TSQM-9m)

Following completion of assessments, subjects' device will be programmed as needed and programming information may be collected.

- In the event of suspected lead migration or to aid programming the subject's device, imaging may be performed to document lead position.
- Any additional instructions related to charging of the device and/or use of Remote Control may be provided.

End of Visit Information:

- Subjects will receive instructions on the use of the device including the Remote Control and charging system, as needed.
- Subjects are to contact the site in an event that any additional intervention is warranted, to report a complaint and/or a suspected adverse event, reprogramming, etc.
- Changes to opioid pain medications are allowed up to End of Study Visit.

11.13. 6-Month Visit (180 ± 30 days)

During the 6-Month Visit, subjects will return to the clinic for study evaluations and programming. Any adverse events since their last study visit will be collected.

The following assessments will be completed as summarized in Table 11.1-1:

- Oswestry Disability Index version 2.1a (ODI v2.1a)
- Short Form Health Survey 36 items (SF-36 v2)
- EQ-5D 5-Level
- Resource Utilization Inventory (RUI)
- Work Productivity (WPAI-SHP v2.0)
- Pain Intensity: NRS
- Pain Intensity: VRS
- Clinical Global Impression of Change (CGI-C)
- Patient Global Impression of Change (PGI-C)
- Percent Pain Relief (PPR)
- Preference Questionnaire
- Treatment Satisfaction Questionnaire for Medication - modified (TSQM-9m)

Following completion of assessments, subjects' device will be programmed as needed and programming information may be collected.

- In the event of suspected lead migration or to aid programming the subject’s device, imaging may be performed to document lead position.
- Any additional instructions related to charging of the device and/or use of Remote Control may be provided.

End of Visit Information:

- Subjects will receive instructions on the use of the device including the Remote Control and charging system, as needed.
- Subjects are to contact the site in an event that any additional intervention is warranted, to report a complaint and/or a suspected adverse event, reprogramming, etc.
- Changes to opioid pain medications are allowed up to End of Study Visit.

11.14. 9-Month Visit (270 ± 30 days)

During the 9-Month Visit, subjects will return to the clinic for study evaluations and programming. Any adverse events since their last study visit will be collected.

The following assessments will be completed as summarized in Table 11.1-1:

- Oswestry Disability Index version 2.1a (ODI v2.1a)
- Short Form Health Survey 36 items (SF-36 v2)
- EQ-5D 5-Level
- Resource Utilization Inventory (RUI)
- Work Productivity (WPAI-SHP v2.0)
- Pain Intensity: NRS
- Pain Intensity: VRS
- Clinical Global Impression of Change (CGI-C)
- Patient Global Impression of Change (PGI-C)
- Percent Pain Relief (PPR)
- Preference Questionnaire
- Treatment Satisfaction Questionnaire for Medication - modified (TSQM-9m)

Following completion of assessments, subjects’ device will be programmed as needed and programming information may be collected.

- In the event of suspected lead migration or to aid programming the subject’s device, imaging may be performed to document lead position.
- Any additional instructions related to charging of the device and/or use of Remote Control may be provided.

End of Visit Information:

- Subjects will receive instructions on the use of the device including the Remote Control and charging system, as needed.
- Subjects are to contact the site in an event that any additional intervention is warranted, to report a complaint and/or a suspected adverse event, reprogramming, etc.

11.15. Year 1 Visit (365 ± 30 days)

During the 1 Year Visit, subjects will return to the clinic for study evaluations and programming. Any adverse events since their last study visit will be collected.

The following assessments will be completed as summarized in Table 11.1-1:

- Beck Depression Inventory (BDI-II)
- Oswestry Disability Index version 2.1a (ODI v2.1a)
- Short Form Health Survey 36 items (SF-36 v2)
- EQ-5D 5-Level
- Resource Utilization Inventory (RUI)
- Work Productivity (WPAI-SHP v2.0)
- Pain Intensity: NRS
- Pain Intensity: VRS
- Clinical Global Impression of Change (CGI-C)
- Patient Global Impression of Change (PGI-C)
- Percent Pain Relief (PPR)
- Preference Questionnaire
- Treatment Satisfaction Questionnaire for Medication - modified (TSQM-9m)

Following completion of assessments, subjects' device will be programmed as needed and programming information may be collected.

- In the event of suspected lead migration or to aid programming the subject's device, imaging may be performed to document lead position.
- Any additional instructions related to charging of the device and/or use of Remote Control may be provided.

The 1 Year Visit is the End of Study Visit and End of Study Action Plan (ESAP) will be followed as described in Section 10.5.

11.16. *Unscheduled Visit*

Subjects may have as many unscheduled visits as required for device-related in-office or procedure visits (e.g., optimization of programming during the programming period) or for evaluation of possible adverse events and if applicable, re-positioning, replacement or explant of a device component. Unscheduled visit information will be captured, as applicable.

11.16.1. Revision or Replacement of Leads, Extensions and/or IPGs

During the course of the study, it is possible that leads may be placed incorrectly, migrate, or malfunction and require repositioning or replacement. It is also possible that the extensions or splitters or IPG may be uncomfortable or malfunction and may require repositioning or replacement. The decision to reposition or replace any device component will be made by the investigator and only if the subject agrees. Subjects not agreeing to a recommended lead revision will be withdrawn from the study but will be included in the intent-to-treat and safety analyses. Subjects agreeing to revision will continue on study and will be followed according to the original study schedule. Effectiveness data from these subjects will be included in the intent to treat analysis. Lead revisions/replacements for the purpose of correcting for migration and/or malfunction must be performed as soon as is reasonably possible following determination of the need for revision/replacement.

The investigator should notify Boston Scientific prior to any study procedures. Any replacements or revisions performed during the course of the study should be recorded in the EDC system, including information about the procedure, device, and/or adverse event if applicable.

Information on assessing revisions or replacements of leads, extensions or IPGs as adverse events is described in Section 20.

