10.1. Point of Enrollment

A subject will be considered enrolled in the study when the Informed Consent Form (ICF) is signed. All enrolled and activated subjects will be included in the study analyses.

If device implantation is unsuccessful, the subject will be followed for 2 weeks post implantation attempt to assess for procedure related adverse events.

10.2. *Withdrawal*

All subjects enrolled in the clinical study (including those withdrawn from the clinical study or lost to follow-up) shall be accounted for and documented. If a subject withdraws from the clinical investigation, the reason(s) shall be reported. If such withdrawal is due to problems related to investigational device safety or performance, the investigator shall ask for the subject's permission to follow his/her status/condition outside of the clinical study.

While study withdrawal is discouraged, subjects may withdraw from the study at any time, with or without reason and without prejudice to further treatment. In all cases of withdrawal or discontinuation, the Investigator will make all reasonable efforts to determine the reason for the subject's withdrawal. Subjects may be discontinued from the study for the various reasons, such as:

- Withdrawal of consent
- A safety concern defined by the Principal Investigator and/or Boston Scientific Neuromodulation (e.g., adverse event)
- Study non-compliance
- Inadequate use of device that may impact study outcomes Subject did not meet inclusion criteria or met an exclusion criterion after signing informed consent
- Surgical intervention that affects the Implantable Pulse Generator (IPG) and/or leads
- Lost to follow-up
- Death of the subject

A subject is considered lost-to-follow-up after 3 unsuccessful contact attempts have been made to reach the subject (including those who relocate but cannot be transferred to another participating site). Staff at the participating site should make a good faith effort to contact the subject with three documented communication attempts, at least one of which must be in writing, sent via a traceable method to inform the subject that the device must programmed per standard of care with commercially approved settings.

Data collected up to the point of subject withdrawal or lost to follow-up may be used for study analysis in accordance with applicable regulations.

Withdrawn subjects will be followed per the End of Study Action Plan as described in Section 10.5.

10.3. *Subject Status and Classification*

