Subjects who provide written informed consent but do not meet all of the study eligibility criteria will not be implanted or activated. These subjects will be deemed as "enrolled but not activated" and their reason for ineligibility will be documented.

Enrolled subjects who are not activated will not count towards the enrollment cap. Subjects who sign consent, meet all eligibility criteria, undergo permanent implant and are activated cannot be replaced.

[REDACTED]

[REDACTED]

[REDACTED]

10.5. *End-of-Study Action Plan*

When each subject completes the 1-Year Visit or withdraws, the subject exits the study and ends study participation. Subjects may continue to use their system per the applicable Directions for Use and will be followed according to standard of care.

If the study is terminated early due to sponsor discretion or due to the discovery of an unexpected, significant, or unacceptable risk/safety concern regardless of how far along the subject has reached in their study follow-up, subjects will be followed according to standard of care. Sites will have 30 days to notify all subjects of study closure.

If device implantation is unsuccessful, the subject will be followed for 2 weeks post implantation attempt to assess for procedure related adverse events. If the device is explanted, the subject will be followed for 30 days post explant to assess for related adverse events.

Device related adverse events and/or deficiencies occurring after study participation, withdrawal from the study, or after the specified timeframe following unsuccessful trials, implant failures, and explants, should be reported to BSN Patient Care at: [contact]. Such complications should not be captured as adverse events in the study.

11. Study Methods

11.1. *Data Collection*

There are a number of different study assessments required at each visit. The data collection schedule is provided in Table 11-1. Full descriptions for all assessments are provided in Section 13.

Table 11.1-1: Data Collection Schedule

| | Screening | Opioid Medication Lock Visit | Baseline Period | Baseline Visit | Implant Procedures (Trial and Permanent) | Activation Visit | Programming Period | Programming Lock Visit | Evaluation Period | 3-Month Visit | 6-Month Visit | 9-Month Visit | 1-Year Visit | Unscheduled Visit |

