|---|----------------|------------------------------|------------------------------|----------------|--|------------------|-------------------------------------|------------------------|-------------------|----------------|----------------|----------------|----------------|-------------------|
| | | Up to 35 days | 14 days post-Medication Lock | | Up to 90 days post-Baseline Visit | Day 0 | Up to 70 days post-Activation Visit | 70 ± 14 days | | 90 + 14 days | 180 ± 30 days | 270 ± 30 days | 365 ± 30 days | End of Study |
| Informed Consent (ICF) | X | | | | | | | | | | | | | |
| Inclusion/Exclusion Criteria Evaluation | → | | | | | | | | | | | | | |
| Demography | | | | X | | | | | | | | | | |
| Medical History | | | | X | | | | | | | | | | |
| Beck Depression Inventory (BDI-II) | | | | X | | | | | | X | | | X | |
| Oswestry Disability Index (ODI v2.1a) | | | | X | | | | | | X | X | X | X | |
| Short Form Health Survey 36 item (SF-36v2) | | | | X | | | | | | X | X | X | X | |
| EQ-5D-5L | | | | X | | | | | | X | X | X | X | |
| Resource Utilization Inventory (RUI) | | | | X | | | | | | X | X | X | X | |
| Work Productivity (WPAI-SHP v2.0) | | | | X | | | | | | X | X | X | X | |
| Pain Intensity (NRS) | | | | X | | | | | | X | X | X | X | |
| Pain Intensity (VRS) | | | | X | | | | | | X | X | X | X | |
| Procedure Information | | | | | X [†] | | | | | | | | | X ^{**} |
| End of Trial Assessment | | | | | X | | | | | | | | | |
| Programming Parameters ^{***} | | | | | X | X | X | X | X | X | X | X | X | X |
| Therapy Rating | | | | | X | → | | | | | | | | |
| Clinician Global Impression of Change (CGI-C) | | | | | | | | | | X | X | X | X | |
| Patient Global Impression of Change (PGI-C) | | | | | | | | | | X | X | X | X | |
| Percent Pain Relief (PPR) | | | | | | | | | | X | X | X | X | |
| Preference Questionnaire | | | | | | | | | | X | X | X | X | |
| Treatment Satisfaction Questionnaire (TSQM-9m) | | | | | | | | | | X | X | X | X | |
| Concomitant Medications (opioid pain medications) | | X | | X | X | X | X | X | X | X | X | X | X | X |
| Adverse Event (AE) | X [‡] | X [‡] | X [‡] | X [‡] | X [‡] | X [‡] | X [‡] | X [‡] | X [‡] | X [‡] | X [‡] | X [‡] | X [‡] | X [‡] |

Healing Period (0-28 days)

Opioid Medications Locked

^{**}For unscheduled visits where procedures are performed.

^{***}Only when device programming is performed.

[†]The device will remain off until the Activation Visit.

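### Withdrawal before Month 3, required after a refused lead revision and permitted on other grounds, leaves activated subjects in the primary analysis without a post-activation pain score

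*Combined protocol and SAP*

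**What the plan says.** **Withdrawal that is required.** Section 11.16.1, on a refused lead revision: "Subjects not agreeing to a recommended lead revision will be withdrawn from the study but will be included in the intent-to-treat" and safety analyses. Subjects who agree to revision stay in the study on their original schedule.

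**Withdrawal that is permitted.** Section 10.2 lists reasons for which a subject may be discontinued. Besides consent withdrawal, loss to follow-up and death, they include a safety concern, study non-compliance, "Inadequate use of device that may impact study outcomes" and "Surgical intervention that affects the Implantable Pulse Generator (IPG) and/or leads".

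**What withdrawal does.** Section 10.5: "When each subject completes the 1-Year Visit or withdraws, the subject exits the study and ends study participation". Section 11.18 likewise follows activated subjects only to the 1-Year Visit or to withdrawal. Section 10.2 adds: "Data collected up to the point of subject withdrawal or lost to follow-up may be used for study analysis". If withdrawal is due to device safety or performance, the investigator asks for "permission to follow his/her status/condition outside of the clinical study".

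**Who is analysed.** Section 10.1: "All enrolled and activated subjects will be included in the study analyses". Section 10.3 bars replacement of activated subjects.

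**When pain is measured.** The NRS row of Table 11.1-1 reads "Pain Intensity (NRS) | | | | X | | | | | | X | X | X | X", that is, the Baseline Visit and then the 3-, 6-, 9-Month and 1-Year Visits. The VRS row has the same pattern. Neither score is scheduled between Baseline and Month 3 or at unscheduled visits.

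**The concern.** The primary endpoint needs a pain score at 3 months and an opioid record. The plan removes some activated subjects before that score is taken, for reasons other than their own refusal to be assessed, and still counts them in the analysis. Refusing a revision, or hardly using the device, is plausibly (not demonstrably) linked to poor benefit, so the missing scores may not resemble the observed ones.

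In a single-arm, open-label trial the responder rate is the main result, and there is no control arm in which the same loss would occur. What is at stake is mainly the accuracy of that rate. The loss is avoidable, because the 3-Month assessment is already in the schedule. Withdrawals after Month 3 do not touch the primary endpoint.

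**Working it through.** The plan shows no withdrawal rate, sample size or alpha in its visible text, so there is no figure of its own to reproduce. The check has two parts.

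**1. Following one subject through the text**

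- The subject is activated, so Section 10.1 places them in the analyses.
- Before Month 3 a lead revision is recommended and refused. Section 11.16.1 requires withdrawal and keeps the subject in the intent-to-treat analysis.
- Sections 10.5 and 11.18 end study follow-up.
- Section 10.2 names data up to withdrawal as usable. By Table 11.1-1 those data hold the Baseline NRS and VRS and no later ones.
- Result: in the analysis, with no post-activation pain score.

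A discretionary discontinuation under Section 10.2 before Month 3 leads to the same result. The one difference is that it depends on how sites and the sponsor use the discretion.

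**2. Size**

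Inputs from Section 12.1.1.1: OPC 40% and margin 0.20, so the null boundary is 0.40 − 0.20 = 0.20. Assumed: r, the responder rate among observed subjects; w, the unobserved share of activated subjects; N; and a one-sided alpha of 0.025.

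*Range of the rate based on measured pain.* It runs from r(1 − w), if none of the unobserved respond, to r(1 − w) + w, if all do. The width is w. With r = 0.50:

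| w | lower | upper |
|---|---|---|
| 2% | 0.50 × 0.98 = 49.0% | 49.0% + 2% = 51.0% |
| 5% | 0.50 × 0.95 = 47.5% | 47.5% + 5% = 52.5% |
| 10% | 0.50 × 0.90 = 45.0% | 45.0% + 10% = 55.0% |

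If the redacted text defines these withdrawals as non-response, there is no range and the rate is the lower figure.

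*Effect of collecting the score.* If a share q of these subjects shows a qualifying response and the measured score counts, the rate is r(1 − w) + wq. With r = 0.50, w = 10% and q = 30%, it is 0.45 + 0.10 × 0.30 = 48%, against 45% under non-response. With w = 2% it is 0.49 + 0.02 × 0.30 = 49.6%, against 49%.

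*Distance from the boundary under non-responder scoring.* r(1 − w) = 0.20 gives w = 1 − 0.20/r: 33% for r = 0.30, 50% for r = 0.40 and 60% for r = 0.50. With r = 0.50 and w = 10% scored as non-response, the exact (Clopper-Pearson) one-sided 97.5% lower limits are:

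| Responders/N (N assumed) | Lower limit |
|---|---|
| 18/40 | 29.3% |
| 27/60 | 32.1% |
| 45/100 | 35.0% |

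All lie above 20%.

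**The case against.** **The deciding text is redacted.** Much of Section 12 is blacked out. A reader might infer that the plan has no rule for these missing outcomes, but the documents do not support that. A redacted rule may well score them. This part of the objection stands in full. Such a rule could settle how a missing score is counted, but it could not supply a score that was never taken.

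**Only one ground is mandatory, and it is narrow.** This stands. It needs an activated subject, a recommended lead revision before Month 3, and a refusal. The Section 10.2 grounds are discretionary, and nothing shows how often any of them would be used.

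**Post-withdrawal follow-up exists.** The contact in Section 10.2 applies to device safety or performance withdrawals, needs permission, lies outside the study and names no pain score. The 30 days after explant in Section 10.5 are for adverse events. The Therapy Rating in Section 13.2.18 is an optional remote-control feature, not the 7-day-recall score. None of these fills the gap.

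**The test could be invalid.** A reader might go further and infer inflated type I error. With N = 100, w = 10%, all withdrawn subjects non-responders and all dropped, the rule of at least 27 responders in 90 would have a true error of 0.053 at a responder rate of 20%, against a nominal 0.016. That requires a completer analysis, whereas Sections 10.1 and 11.16.1 include these subjects. The figure does not describe the visible plan.

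**Sections 10.2 and 11.16.1 are in flat conflict over surgery.** That is too strong. A permissive general list and a specific rule can be read together. But Section 10.2 makes no exception for revisions, while Section 11.16.1 keeps subjects who agree to revision in the study and Section 11.16.2 allows revisions through Month 3. Sites could treat like subjects differently, so the sections must be reconciled.

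**Conclusion.** The point holds in limited form. As written, the plan requires withdrawal after a refused lead revision, permits it on other investigator or sponsor grounds, and in both cases ends collection of the primary pain score for activated subjects it keeps in the analysis. This follows from visible text and does not depend on what is redacted.

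The size is a range of width w in the responder rate based on measured pain. The share w is unknown and may be small; the values 2% to 10%, the 50% observed rate, N and alpha are all assumptions. At the assumed values examined the conclusion against the 20% boundary does not change, and it is unlikely to change in practice. The gain is accuracy of the reported rate. The change is worth making because it is cheap; confidence is medium, chiefly because the number affected cannot be known from the documents.

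**What to change.** 1. In Sections 10.2, 10.5 and 11.16.1, state that a refused revision, or any other discontinuation not due to withdrawal of consent, loss to follow-up or death, does not by itself end outcome collection. Activated subjects who still consent complete the already scheduled 3-Month pain score and opioid record, with clinical care unchanged. Wording it this way avoids fixing some Section 10.2 grounds while leaving the same gap under others.
2. Use the measured score in the intent-to-treat responder rate according to the plan's own scoring rule, after checking the redacted text, and report a sensitivity analysis that counts these subjects as non-responders.
3. Reconcile the IPG and lead surgery ground in Section 10.2 with Sections 11.16.1 and 11.16.2 by a cross-reference.

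The cost is protocol wording, a check of the analysis text, one added sensitivity analysis, and one already scheduled visit for what may be a few subjects. The reported rate may shift slightly, in a direction that depends on the scoring rule.
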